10.1 Determination of Sample Size

No formal sample size calculation was made. The number of patients expected to participate in this study was calculated from estimated enrollment rates from other carcinoid cancer trials employed in the LX1606 clinical program.

10.2 Analysis Populations

Per protocol: A Per Protocol population will consist of those patients that receive study treatment and have no major protocol violation that would interfere with the collection or interpretation of the efficacy data. The primary analyses of efficacy will be based on the safety population; the per-protocol population will be used in a supplemental manner.

Safety: The safety population consists of all patients receiving any fraction of a dose of study drug during this study.

10.3 Study Endpoints

10.3.1 Primary and Secondary Endpoints

The primary endpoint is to evaluate the long-term safety and tolerability of orally administered telotristat etiprate.

The secondary endpoint is to evaluate changes in patients' QOL over 84 weeks of therapy.

10.3.2 Safety Endpoints

Safety endpoints are as follows:

- Incidence of TEAEs, suspected adverse reaction, AEs leading to discontinuation from the study, SAEs, and deaths
- Actual and change from Baseline in clinical laboratory results
- Actual and change from Baseline in vital signs results
- Actual and change from Baseline in physical examinations
- Actual and change from Baseline in ECG findings

10.4 Statistical Methods

Descriptive analysis methods will be used to summarize the data. Continuous variables will be summarized by the N, mean, standard deviation, median, minimum, and maximum values. Categorical variables will be summarized as counts and related percentages. Data tabulations will be categorized by the treatment received on Day 1 of this study, where appropriate, and combined across all treated patients. All data will be listed.

Primary analyses of the data will be based on the Safety population which includes all patients treated with any fraction of study drug during this study. Supportive analyses of the efficacy data will be made on a Per Protocol population. This dataset will include the Safety population, but limited to those patients that have at least one assessment post Day 1 and do

not have any protocol violations that would interfere with collection or interpretation of the data. The Per Protocol analysis will be applied to the QOL measures, subjective global assessment, and plasma 5-HIAA values.

Data will be summarized per study visit as the actual (raw) outcomes and change from Baseline scores, where applicable. Day 1 of this study will serve as the Baseline assessment.

10.4.1 Efficacy Analyses

All efficacy and PD variables will be summarized descriptively and listed.

Statistical tests and estimates of within patient effects for these measures will be derived from application of a mixed linear model with repeated measures. The model will be generalized to handle missing data and specific to the measurement properties of the dependent variable. There is no plan to impute data for missing observations for any variable. Non-parametric methods will be used to supplement the tests and estimates from the mixed linear model.

Exploratory analyses of treatment group differences may be performed by use of propensity score models. The treatments groups will correspond to how patients were dosed on Day 1 of this study.

10.4.2 Safety Analyses

Statistical analysis of the safety data will involve examination of the descriptive statistics and individual patient listings for any effects of study treatment on clinical tolerability and safety. Reporting of these data will be based on the Safety population. Summaries will be prepared by treatment group (corresponding to the LX1606 dose given on Day 1), pooled across all patients, and as needed, by study visit. All safety data will be listed.

Treatment-emergent adverse event summaries will include the overall incidence (by system organ class and preferred term), events by maximum intensity, events by relationship to study treatment, events leading to discontinuation of study drug, events leading to study discontinuation, and SAEs.

Vital signs, ECG, and laboratory parameters (hematology, chemistry, and urinalysis) will be summarized descriptively at each time point. Actual and change from Baseline data will be calculated and summarized. In addition, shift table analysis will be applied to the laboratory data and summarized.

10.4.2.1 Adverse Events

All AEs will be coded and listed by body system and preferred term based on the Medical Dictionary for Regulatory Activities (MedDRA). Summaries using descriptive statistics will be provided for treatment-emergent AEs, drug-related AEs and AEs by intensity. Treatment-

emergent AEs are those events not present at Baseline, but occurring after the start of study drug, or if existing at Baseline, increasing in intensity after initiation study drug. Summaries made by intensity will select the event with the highest intensity when multiple occurrences of the same event are reported for the same patient. In a similar manner, summaries prepared by drug relationship will select the event with the greatest degree of relationship when a study reports multiple occurrences of the same event. On-study deaths will be reported for deaths occurring during the active phase of the treatment period and 30 days after stopping study drug. Also, deaths occurring outside the 30-day window, but secondary to an AE reported within the 30-day post treatment period, will be reported as well.

Listings will be provided for deaths, SAEs, and discontinuations due to AEs. Additional summaries or listings of AEs may also be provided.

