9.2 Serious Adverse Events (SAEs)

An SAE is defined as any event that results in any of the following outcomes:

1. Death
2. A life-threatening adverse event;
3. Inpatient hospitalization or prolonging of an existing hospitalization (see [Section 9.2.1](#) for information on hospitalization as an SAE);

4. A persistent or significant incapacity or substantial disruption of the ability to conduct normal life functions; or
5. A congenital anomaly/birth defect.

Important medical events that may not result in death, be life-threatening, or require hospitalization may be considered serious when, based upon appropriate medical judgment, they may jeopardize the subject and may require medical or surgical intervention to prevent one of the outcomes listed above.

Any SAE must be reported by telephone or facsimile within 24 hours of discovery of the event. Investigators should not wait to receive additional information to fully document the event before notifying the Sponsor of an SAE at:

Sites in North America must report to:

Safety Data [contact]

Email address (in case of fax failure): [contact]

Sites outside North America must report to the country specific toll-free fax numbers identified below:

Australia: [REDACTED]
Belgium: [REDACTED]
Brazil: [REDACTED]
France: [REDACTED]
Germany: [REDACTED]
Israel: [REDACTED]
Italy: [REDACTED]
Netherlands: [REDACTED]
Spain: [REDACTED]
Sweden: [REDACTED]
United Kingdom: [REDACTED]

Email Address (in case of fax failure): [REDACTED]

The telephone report should be followed by full written summary detailing relevant aspects of the SAE in question using the provided SAE report form. Where applicable, information from relevant hospital case records and autopsy reports should be obtained. The SAE should also be recorded on the AE page of the patient's CRF.

An SAE that occurs after completion of the study but, in the opinion of the Investigator, is related to the study medication, should be reported as described for an SAE. If an AE does not meet the regulatory definition of "serious" but is considered by the Investigator to be

related to the study medication and of such clinical concern as to influence the overall assessment of safety, it must be reported as defined for an SAE.

All patients (including discontinued patients) with a SAE must be followed until the event resolves or reaches a new Baseline, but for a minimum of 30 days after the last dose of study drug.

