¹Eligibility will be determined at last visit of the original protocol; Day 1 will replace the next scheduled visit in the original protocol schedule. Visits should coincide with LAR injections for those patients receiving SSA therapy.
²Females of child-bearing potential only. ³Brief physical examination only (symptom-oriented, including weight). ⁴Visit to be performed for subjects who withdraw early and will not return for a 2-week follow-up visit; in all other cases the End-of-Study (EOS) visit should be performed followed by the follow-up visit 2 weeks after the final dose. ⁵To be performed only if evaluation at EOS is abnormal. ⁶All patients will receive LX1606 for at least 52 weeks and may continue treatment in the trial until such time telotristat etiprate has received regulatory approval to be marketed and is available via prescription or until 31 March 2017, whichever occurs first. Patients who reach this timeline event will be deemed to have completed the Treatment Period and will advance to the EOS visit, regardless of where they are in the visit schedule and when their last study visit occurred. The EOS visit should be performed within 21 calendar days following the completion of the Treatment Period.

14. Appendix B – Amount of Blood to be Collected from Each Patient

Assessment		Sample volume (mL)	Number of samples*	Estimated total volume (mL)
Safety	Hematology	2	17	34
	Blood chemistry	6	17	102
Other	CgA	2	5	10
Pharmacodynamic	Plasma 5-HIAA	4	17	68
			Total	214
*Maximum number of samples is indicated				

16. Appendix D – EORTC QLQ - GI.NET21

ENGLISH

EORTC QLQ – GI.NET21

Patients sometimes report that they have the following symptoms or problems. Please indicate the extent to which you have experienced these symptoms or problems during the past week. Please answer by circling the number that best applies to you.

During the past week:		Not at all	A little	Quite a bit	Very much	
31.	Did you have hot flushes?	1	2	3	4	
32.	Have you noticed or been told by others that you looked flushed/red?	1	2	3	4	
33.	Did you have night sweats?	1	2	3	4	
34.	Did you have abdominal discomfort?	1	2	3	4	
35.	Did you have a bloated feeling in your abdomen?	1	2	3	4	
36.	Have you had a problem with passing wind/gas/flatulence?	1	2	3	4	
37.	Have you had acid indigestion or heartburn?	1	2	3	4	
38.	Have you had difficulties with eating?	1	2	3	4	
39.	Have you had side-effects from your treatment? (If you are not on treatment please circle N/A)	N/A	1	2	3	4

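### Read literally, the on-study death rule leaves out a death more than 30 days after the last dose if the fatal AE was reported during treatment, but counts it if the AE was reported in the 30 days after stopping

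*Protocol*

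**What the plan says.** Section 10.4.2.1 of the protocol (Amendment 4) sets the rule in two clauses. The first reads "On-study deaths will be reported for deaths occurring during the active phase of the treatment period and 30 days after stopping study drug". The second adds "deaths occurring outside the 30-day window, but secondary to an AE reported within the 30-day post treatment period". The same two sentences stand in the Amendment 2 and Amendment 3 texts.

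Section 10.3.2 makes deaths part of the safety endpoints: "Incidence of TEAEs, suspected adverse reaction, AEs leading to discontinuation from the study, SAEs, and deaths". It attaches no time window. Section 4.1 gives long-term safety and tolerability as the primary objective.

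Three other provisions bear on the point:

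- Section 9.2, on follow-up: "All patients (including discontinued patients) with a SAE must be followed until the event resolves or reaches a new Baseline", with 30 days after the last dose as the minimum.
- Section 10.4.2.1, next paragraph: "Listings will be provided for deaths, SAEs, and discontinuations due to AEs", again with no window. Section 10.4.2 adds that all safety data will be listed.
- Appendix A, footnote to the Schedule of Events: "The EOS visit should be performed within 21 calendar days following the completion of the Treatment Period".

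**The concern.** The second clause exists to catch deaths that come late but trace back to an event in the observation window. It identifies that event only by its being reported after treatment ended. The first clause has just distinguished the active phase of treatment from the 30 days after stopping, so the post-treatment period cannot naturally be read to include treatment itself.

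The gap therefore covers a foreseeable sequence: a serious AE reported on drug, drug stopped, and death more than 30 days later. The count can err in one direction only, downwards, and it does so for events reported while the patient was still taking study drug. At stake is the summarised incidence of a named safety endpoint in a study whose primary purpose is long-term safety.

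**Working it through.** The plan gives no figure to reproduce, so the check is to apply the two clauses to each case. Suppose the last dose is on Day 310. The 30-day window then ends on Day 310 + 30 = Day 340.

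| Case | Fatal AE reported | Death | Clause 1 | Clause 2 | Counted? |
|---|---|---|---|---|---|
| A | Day 300, on treatment | Day 345 (35 days after last dose) | No | No | No |
| B | Day 320, 10 days after last dose | Day 345 | No | Yes | Yes |
| C | Any time up to death | Day 330 (20 days after last dose) | Yes | Not needed | Yes |
| D | Began Day 300, first reported Day 320 | Day 345 | No | Yes | Yes |
| E | After Day 340 | Later still | No | No | No |

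A and B have the same death date and the same last dose, and differ only in when the AE was reported. A is left out and B is counted. That is the inconsistency. E is outside the rule on any reading.

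D shows that the test is the report date, not the onset date. An AE that began on drug but was first reported at an End-of-Study visit, which may fall up to 21 days after the Treatment Period, satisfies the second clause. The gap is therefore confined to AEs reported before drug was stopped. For serious events it is still a real class, because Section 9.2 requires SAEs to be reported within 24 hours of discovery. An SAE discovered on drug will normally be reported on drug.

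The number of deaths affected cannot be computed, because the documents give neither a death rate nor the time from stopping drug to death. An assumption can only illustrate how large the affected share of one class might be. Take fatal AEs reported on treatment, with drug stopped at that report and an exponential time from stopping to death. The share dying after day 30 is exp(−30 × ln 2 / median):

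- median 14 days: exp(−30 × 0.693 / 14) = 0.23
- median 30 days: exp(−30 × 0.693 / 30) = 0.50
- median 60 days: exp(−30 × 0.693 / 60) = 0.71

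The medians and the exponential form are not in the documents. These shares are not estimates of how far the total death count is understated.

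**The case against.** The strongest reply is that the intent is obvious. The second clause is worded as an addition to the first, no sentence says that other deaths are to be withheld, and a sensible programmer would include case A. That is probably what the authors meant. It makes the correction uncontroversial, but it does not make the sentence right: an analysis that followed the protocol's wording would inherit the gap.

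The second reply is the listings, and it stands in large part. A reader might infer that case A deaths are lost from the report. The documents do not support that. Deaths and SAEs are to be listed without a window, all safety data are to be listed, and the on-treatment AE remains in the TEAE summary and, if serious, in the SAE summary. What goes wrong is the count, and a listing does not correct a summarised incidence.

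Two other inferences also fail. A reader might conclude that every late death from an AE that arose on treatment is omitted; case D shows otherwise, since the rule turns on reporting. A reader might also take the omitted class to be the one most likely caused by the drug. Nothing in the protocol establishes this. The fatal SAEs described in Section 3.2.2 for the two carcinoid syndrome Phase 2 studies were disease or neoplasm progression, and neither was reported as related to study drug.

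Finally, late deaths may not all be captured. Section 9.2 makes capture likely by following SAEs to resolution or a new Baseline, but a patient whose event reaches a new Baseline can leave follow-up once the 30-day minimum has passed.

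**Conclusion.** The point holds as a defect in a rule that the protocol itself fixes, not as a detail left to a later document. Applied literally, Section 10.4.2.1 leaves out of the on-study death count a death more than 30 days after the last dose whose AE was reported on treatment, while counting the same death if the AE was reported in the following 30 days. No other section repairs this.

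The effect is a one-directional understatement of the summarised incidence of deaths. Its size cannot be quantified from the documents. The conclusion rests on the literal wording being used for the count and on at least some such late deaths being known to the study.

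Severity is moderate to minor. A reader might see a defect that invalidates the safety analysis, but the study is open-label, the safety analysis is descriptive, no test or sample size depends on the rule, and the individual deaths remain visible in the listings.

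**What to change.** Replace the second clause of the rule in Section 10.4.2.1 with wording such as: *deaths occurring more than 30 days after the last dose, but secondary to an AE with onset from the first dose in this study through 30 days after the last dose, will also be reported.*

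This brings case A into the count and leaves B, C and D counted. Moving from report date to onset date also stops the result depending on how soon an event was reported. For a condition present at Baseline that worsens, the date of worsening should serve as onset, in line with the treatment-emergent definition in the same section.

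The cost is one sentence and a small change to the table program. It requires no additional visits or procedures. The death count may come out slightly higher. It should be settled before deaths are tabulated.

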10.4.2.2 Clinical Laboratory Parameters

Laboratory results will be reported in conventional units in all tables, figures, and listings. Laboratory results falling out of the normal range will be marked as high or low in the listings. Actual and changes from Baseline (Day 1) in clinical laboratory results will be summarized by using descriptive statistics. Summaries of shifts from Baseline to abnormal clinical laboratory results will also be provided. Actual and change from Baseline in chromogranin A levels will be summarized descriptively as well.

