3.2.3 Ongoing Studies

LX1606.1-301-CS is intended to evaluate patients who are currently on a background of SSA therapy and still experiencing breakthrough symptoms such as a frequency of BMs ≥ 4 per day on average: (1) the efficacy of telotristat etiprate on reducing the number of BMs; (2) the efficacy of telotristat etiprate on a number of clinically relevant secondary endpoints; and, (3) the safety of telotristat etiprate over the 12-week double-blind portion (Treatment Period) of the study. Upon completion of the Treatment Period, patients will continue into a 36-week open-label Extension Period.

LX1606.1-303-CS is intended to evaluate patients with carcinoid syndrome whose primary symptoms are not GI related and may be naïve to SSA therapy: (1) the safety of telotristat etiprate over the 12-week double-blind portion (Treatment Period) of the study; (2) percent (%) change from Baseline in 24-hour u5-HIAA levels at Week 12; (3) the effects of telotristat etiprate on a number of clinically relevant secondary endpoints. Upon completion of the Treatment Period, patients will continue into a 36-week open-label Extension Period.

Detailed information regarding the ongoing clinical studies can be found in the Investigator Brochure.⁸

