5.1 Overall Study Design

The study will be conducted as a multicenter, open-label, long-term extension study to further evaluate long-term safety and tolerability of telotristat etiprate.

Patients currently participating in any LX1606 Phase 2 CS study may enter into this extension study upon institutional or local approval of the protocol. Patients participating in a Phase 3 CS study may enter into this extension study at the Week 48 visit. All patients who enter into this extension study will be exempt from any follow-up visit required by the original study and will not experience an interruption in study drug due to the transition from the original protocol to LX1606.1-302-CS.

Following confirmation of eligibility, patients will complete a series of visit assessments in order to establish Baseline symptoms. Patients will then continue on open-label LX1606 at the same dose level identified in the original study.

All patients will receive telotristat etiprate for at least 52 weeks and may continue treatment in the trial until such time telotristat etiprate has received regulatory approval to be marketed and is available via prescription or until 31 March 2017, whichever occurs first. Patients who reach this timeline event will be deemed to have completed the Treatment Period and will advance to the End-of-Study (EOS) visit as identified in [Appendix A – Schedule of Events](#), regardless of where they are in the visit schedule and when their last study visit occurred.

Upon completion, all patients will be required to complete a 14-day Follow-up Period, during which no study drug will be administered.

Downward dose adjustment will be permitted during the study if evidence of intolerability emerges. Patients who experience intolerability at the 250 mg tid dose level must be discontinued from the study. Patients may return to the previous dosing at the discretion of the Investigator and in consultation with the Medical Monitor.

A Data Safety Monitoring Board (DSMB) will review safety data quarterly throughout the study.

6. Study Population

Adult patients who are currently participating in ongoing Phase 2 or Phase 3 telotristat etiprate CS clinical protocols will be enrolled into the study. Up to 130 patients are expected to enroll in this study. Approximately 50 sites worldwide will participate in the study. Patients

may continue allowed medications as background therapy provided they remain on stable-doses throughout the Treatment Period.

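### Laboratory change and shift tables start from an on-drug Baseline, so for ALP (and GGT, if measured) they describe only what happens after entry to the extension

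*Protocol*

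**What the plan says.** Section 10.4 sets one Baseline for the whole study: "Day 1 of this study will serve as the Baseline assessment". Section 10.4.2.2 repeats it for laboratory data, "Actual and changes from Baseline (Day 1) in clinical laboratory results will be summarized by using descriptive statistics", and adds "Summaries of shifts from Baseline to abnormal clinical laboratory results will also be provided". Section 10.4.2 covers vital signs, ECG and laboratory parameters by time point: "Actual and change from Baseline data will be calculated and summarized". It also states "All safety data will be listed", and Section 10.4.2.2 has out-of-range results marked in the listings.

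On entry, Section 5.1 states: "Patients participating in a Phase 3 CS study may enter into this extension study at the Week 48 visit". Entrants "will not experience an interruption in study drug due to the transition from the original protocol". Section 3.2.3 describes a 12-week double-blind period in both Phase 3 studies and then: "Upon completion of the Treatment Period, patients will continue into a 36-week open-label Extension Period". In the Schedule of Events (Appendix A) the first chemistry draw is at Day 1, so this study itself collects no pre-drug value.

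On the signal, Section 3.2.2 reports that mean ALP and GGT in study LX1606.1-202-CS (23 patients) stayed above that study's own Baseline in both its Core and Extension Phases, without clinical consequences judged relevant.

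**The concern.** The primary objective is long-term safety and tolerability. The two displays a safety reader uses to see whether a laboratory value has moved are change from Baseline and the shift table. Here both start from a value taken on drug. If ALP or GGT rises early and then stays level, the movement lies before Day 1 and drops out of both displays. This matters most for ALP and GGT because they are the only laboratory exception the current protocol reports in patients with carcinoid syndrome. Study 202 found it by comparing later values, including those in its open-label phase, with that study's own Baseline. The extension plan provides for no such comparison.

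**Working it through.** The protocol makes no formal sample size calculation and gives no figure on this point to reproduce. The check is of exposure at Baseline and of how a stable rise is tabulated.

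**Scheduled drug exposure at Day 1, Phase 3 entrants** (Sections 3.2.3 and 5.1)
- Drug throughout: 12 + 36 = 48 weeks.
- Placebo in the double-blind period: 48 − 12 = 36 weeks.
- Phase 2 entrants: exposure at Day 1 is not given.

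**Share of total scheduled drug time that precedes Baseline**, prior / (prior + weeks in the extension)
- Extension Week 48: 36/84 = 42.9% and 48/96 = 50.0%.
- Extension Week 84: 36/120 = 30.0% and 48/132 = 36.4%.

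These are shares of time on drug. They do not measure any missed change.

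**What a stable rise looks like.** Suppose the rise is complete by Day 1. The later value and the Day 1 value then have the same expectation, so expected change is zero. A patient carried above the ULN is high at Day 1 and high later, which is a high-to-high cell.

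A simulation of 100,000 patients illustrates this. All its inputs are assumed and none comes from the documents: ULN 120, pre-drug mean 95 (SD 20), within-patient error SD 5.

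| Stable rise | Mean change from Day 1 | Mean change from pre-drug | Normal-to-high from Day 1 | Normal-to-high from pre-drug | High flag at visit |
|---|---|---|---|---|---|
| 10% | about 0 | +9.5 | 4.0% | 13.8% | 24.7% |
| 25% | about 0 | +23.7 | 4.4% | 36.6% | 48.2% |
| 50% | about 0 | +47.5 | 2.8% | 65.7% | 76.9% |

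The shifts from Day 1 are measurement noise near the ULN. The high-flag column is the same under either Baseline. The rise therefore remains visible as a level but not as a movement.

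**Why any added table should use single scheduled visits.** Appendix A has 14 chemistry draws from Week 12 to Week 168, plus the end-of-study visit, making 15 after Day 1. Assume no drug effect and independent normal within-patient variation. Expected change from one pre-drug value is then 0 at any single visit, but +1.74 within-patient SD for the highest of 15. With an assumed true mean of 0.9 × ULN and a within-patient CV of 10%, a false normal-to-high shift occurs in 11.6% of patients per visit but 76.5% for the highest of 15. At 0.8 × ULN the figures are 0.6% and 8.9%.

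**The case against.** The strongest reply is that nothing here is inconsistent. Day 1 is used as Baseline throughout, and it is the right reference for asking what happens during the extension. Early change belongs to the parent studies, which assess safety against placebo over 12 weeks. The remedy leaves the Day 1 tables in place, so it amounts to one more output, which an SAP could add. The signal is also thin. Study 203 reported no laboratory trend of clinical significance. The Amendment 3 text (Section 3.2.1) reports no ALP change in the 14-day multiple-dose study in healthy volunteers. GGT is not named in the chemistry panel of Section 8.2.2.

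Much of this stands, and it keeps the point small. Two things remain. First, the Baseline rule is written into the protocol. Change from pre-drug to an extension visit falls between the parent-study reports and these tables. Second, the other safeguards do not supply it. Actual values and flags show a level. Entry review (Sections 6.2 and 8.2.2.1) addresses clinically significant abnormalities, so a milder rise can pass. All three hepatic follow-up triggers in Section 8.2.2.1 require ALT or AST above 3 × ULN, so an isolated ALP or GGT rise meets none of them.

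A reader might infer that the plan hides a liver signal. The documents do not support that: actual values are summarised at each time point, all safety data are listed, and values outside the normal range are flagged. A reader might also infer that entrants had 36 to 48 weeks of drug without any gap. Section 5.1 rules out only an interruption caused by the transition. Continuity during the parent study is not stated.

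**Conclusion.** The point holds in a limited form. Sections 10.4 and 10.4.2.2 fix an on-drug laboratory Baseline, at a scheduled 36 to 48 weeks of drug for Phase 3 entrants. The change and shift tables therefore cannot show a rise since drug was started. For ALP and GGT this serves the long-term safety objective poorly.

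The size of any missed change cannot be computed. Study 202's rise is reported without magnitude, time course or arm split, and the protocol gives no Phase 3 ALP or GGT result. It would be wrong to read the 30% to 50% drug-time shares as the portion of a rise that is lost, or the simulated rises as expected values. The conclusion rests on scheduled exposure and on a rise that is stable by Day 1. A rise that continues or begins after entry would still show against Day 1. This is a worthwhile improvement and does not invalidate the planned summaries.

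**What to change.** In Section 10.4.2.2 keep the Day 1 summaries. Add descriptive by-visit change and normal/high shift tables for ALP, and for GGT if it is in the chemistry panel. The reference is the last parent-study value before the first active dose. For patients who started on placebo, this is the last value before open-label drug. Use scheduled-visit values only, and exclude unscheduled repeats and highest-on-treatment values for the reason shown in the working. Express results as multiples of ULN if laboratories or reference ranges differ between studies, because Section 8.2.2 establishes a central laboratory for this study only.

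The cost is one change and shift table per analyte and a merge of pre-drug values that the sponsor should hold from its own parent studies. No visit, blood draw or assay is added. The downside is interpretive. The tables are uncontrolled and cover only patients who entered and stayed on study, so they cannot separate a drug effect from disease progression or liver metastases. They should be labelled descriptive.
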